3.3. Benefit/Risk Assessment

More detailed information about the known and expected benefits and risks and reasonably expected adverse events of GSK2831781 may be found in the IB.

3.3.1. Risk Assessment

| Potential Risk of Clinical Significance | Summary of Data/Rationale for Risk Refer to GSK2831781 IB for details. | Mitigation Strategy |
|---|--|---|
| Investigational Medicinal Product (IMP) [GSK2831781] | | |
| Neutropaenia | 
Non-clinical:
 
In the repeat dose IV and SC studies in monkeys, marked decreases in absolute neutrophils counts were observed in animals given ≥ 30 mg/kg/week, without clinical sequelae. Neutropenic nadir is observed approximately 4 weeks after start of dosing and is considered to be reversible based on the transient nature of neutropenia observed in the 26-week repeat dose study and the apparent strong adaptive response in the bone marrow of animals in the 4-week study, both in the presence of high systemic GSK2831781 exposure.
 
Clinical:
 
No neutropenia, or trends towards reduced neutrophil counts, were observed in the FTIH study (200630) in healthy volunteers or patients with plaque psoriasis, up to a maximum single dose of 5 mg/kg.
 | 
Exclusion criteria for low neutrophil counts ($< 1.5 \times 10^9/L$) at baseline.
 
Neutrophil count and adverse events (AE)/serious adverse events (SAEs) related to neutropaenia will be monitored.
 
Haematological stopping criteria.
 
Investigators should manage participants as clinically indicated if neutropaenia is seen.
 |
| Infection | 
Non-clinical:
 
No specific studies have been conducted in
 | 
Appropriate exclusion criteria for history of e.g. tuberculosis (TB) (screening for latent infection
 |

| Potential Risk of Clinical Significance | Summary of Data/Rationale for Risk Refer to GSK2831781 IB for details. | Mitigation Strategy |
|--|---|--|
| | 
nonclinical species to investigate the effect of GSK2831781 on response to viral or bacterial infection.
 
In the 26-week study, natural killer cells were lower (down to 0.1X pre-study values) in 4 of the 8 monkeys dosed at 100 mg/kg/week from Day 29, although levels were at or near the overall pre-study and control group values.
 
A significant proportion of newly activated T cells express LAG3, and therefore T cell proliferation upon encounter with an infectious agent may be inhibited by GSK2831781 if exposure is at the same time. However, it has been demonstrated that in healthy participants only a small proportion of central memory T cells express LAG3, so there is low risk of eliminating central memory of anti-infectious immune response against future encounter.
 
Clinical: No clinical concerns regarding infections were identified in the FTIH study (200630).
 | 
included) or other relevant chronic infectious disease [e.g. Hepatitis B virus (HBV) and Hepatitis C virus (HCV), Human Immunodeficiency Virus (HIV)]. In addition, participants with a recent infection or evidence of significant active infection will be excluded from the study.
 
Participants will not be allowed to receive live vaccines within the 4 weeks prior to Day 1 or during the study until the end of Follow-Up. Investigators are expected to follow local and/or national guidelines with respect to vaccinations, including against influenza and pneumococcus. If indicated, non-live vaccines may be administered based on a treating physician assessment of the benefit:risk (e.g., risk of theoretical decreased responsiveness).
 
Investigators will be advised to counsel participants regarding implications for foreign travel, including possible impact on vaccinations and theoretical risks associated with travel to areas of high endemic infection while exposed to GSK2831781. Prior to consenting, participants will be asked to consider whether any impact this might have on their lifestyle would affect their decision to participate in the study.
 |

| Potential Risk of Clinical Significance | Summary of Data/Rationale for Risk Refer to GSK2831781 IB for details. | Mitigation Strategy |
|---|---|--|
| | | Close monitoring of participants for infections will be continued up to the Follow-Up visit, and supportive therapy (including anti-infectives) provided as clinically indicated. |
| Infusion reaction/hypersensitivity | 
Non-clinical: No evidence to date.
 
Clinical: No infusion reactions or hypersensitivity to GSK2831781 were observed in the FTIH study (200630).
 | 
IMP will be administered by clinical staff at clinical sites with appropriate staff training and facilities for the emergency management of hypersensitivity, angioedema and anaphylaxis. Participants will be resident in the clinical unit for 24 hours following start of IMP administration.
 
Exclusion criteria, stopping criteria and appropriate treatment for hypersensitivity reactions.
 |
| Local injection site reaction | 
Non-clinical: A dose-related increase in incidence and/or severity of mononuclear cell perivascular infiltration was observed at SC injection sites of monkeys given ≥ 30 mg/kg/week. Partial recovery in females and full recovery in males at 30 mg/kg/week was observed after 17 weeks off-dose. Not seen with IV administration.
 
Clinical: No reactions were observed following IV administration in the FTIH study (200630).
 | Participants will be resident in the clinical unit for 24 hours following start of IMP administration, and injection sites will be monitored. Any adverse reactions will be managed appropriately and monitored until resolution. |

| Potential Risk of Clinical Significance | Summary of Data/Rationale for Risk Refer to GSK2831781 IB for details. | Mitigation Strategy |
|--|---|---|
| Immunogenicity | 
Non-clinical: Administration of GSK2831781 to monkeys leads to an ADA response which is more prevalent at lower doses and is associated with a reduction in GSK2831781 systemic exposure.
 
Neutralizing ADA, observed in one animal given 100 mg/kg/week SC in the 26-Week GLP study, correlated with decreased GSK2831781 plasma concentrations and were associated with immune complex mediated clinical pathology changes and increased heart rate, which were transient and of minimal magnitude.
 
Immunogenicity in nonclinical species is not predictive of the potential for immunogenicity in humans
 
Clinical: Pre-existing ADAs and post-dosing ADA have been identified in humans. No adverse reactions or alterations in PK associated with immunogenicity were observed in the FTIH study 200630.
 | 
Safety and tolerability is being assessed in participants (including clinical chemistry, haematology, AEs, hypersensitivity reactions).
 
Immunogenicity and the impact, if any, on PK and safety parameters will be monitored.
 |
| Cytokine release syndrome (CRS) | 
Non-clinical: Hyper-immune activation leading to activation of the innate immune system is only a theoretical
 | 
Appropriate monitoring for clinical symptoms associated with cytokine release such as fever, nausea, chills, hypotension, tachycardia,
 |

| Potential Risk of Clinical Significance | Summary of Data/Rationale for Risk Refer to GSK2831781 IB for details. | Mitigation Strategy |
|---|--|---|
| | 
safety concern, as there is no in vitro and in vivo evidence of cytokine release associated with LAG3 and the T cell depletion mechanism.
 
GSK2831781 did not induce cytokine release in the human in vitro assay when using a soluble or immobilised format or in the 4-week study in monkeys.
 
As GSK2831781 is expected to induce ADCC, this may lead to cytokine release due to cell lysis. However, a low proportion of T cells express LAG3, therefore the risk of this is expected to be lower than less targeted depleting mAbs.
 
Clinical: No CRS was observed in the FTIH study 200630. There were minor transient increases in serum Tumour Necrosis Factor (TNF)-α concentrations between 6-48 hours after dosing at all dose levels, but no dose-response relationship, and the magnitude of these rises was not clinically relevant. There were no meaningful changes to serum Interleukin (IL)-6, IL-8, Interferon (IFN)-γ or Granulocyte-colony stimulating factor (G-CSF).
 | 
asthenia, headache, rash, tongue and throat swelling, and dyspnoea, during and for an appropriate period after dosing.
 
Participants will be resident in the clinical unit for 24 hours following start of IMP administration. Participants will be informed in the Informed Consent Form (ICF) to seek prompt medical advice should symptoms indicative of CRS occur, particularly within 72 hours of dosing. Initially, dosing episodes will be separated by a minimum of 22 hours, until at least 3 participants have been dosed in one of the strata.
 
Study site to include facilities and staff training expertise for emergency care/resuscitation.
 |

| Potential Risk of Clinical Significance | Summary of Data/Rationale for Risk Refer to GSK2831781 IB for details. | Mitigation Strategy |
|--|---|---|
| Autoimmune-like reactions | 
Non-clinical: A small percentage of regulatory T cells express LAG3. The clinical relevance of this minority subset of T cells in the pathogenesis of autoimmune reactions is unknown.
 
In the 4-week study minimally increased percentages of subpopulations of regulatory T cells were noted on Day 29 at 100 mg/kg/week IV, which was not observed in monkeys administered 100 mg/kg/week SC. No changes in regulatory T cells were observed in the 26-week study.
 
Increases in anti-keyhole limpet hemocyanin (KLH) immunoglobulin (Ig)M and IgG responses, which were not adverse, were noted after each KLH injection (administered during Weeks 16 and 19) in monkeys given 30 or 100 mg/kg/week for 26-weeks compared to responses in control animals, which persisted in the 30 mg/kg/week group at 12-weeks off-dose. Following an off-dose period of 47 and 50 weeks administration of neoantigen tetanus-toxoid (TT) injection to animals previously administered 30 mg/kg/week, resulted anti-TT IgG antibody levels which were similar to control animals.
 | 
Exclusion criteria for uncontrolled medical conditions or any background medical history that the investigator (in consultation with the GSK Medical Monitor) considers would put the participant at unacceptable risk.
 
Participants will undergo regular assessment until GSK2831781 has been cleared and LAG3+ cells expected to replete. AEs that could be related to autoimmunity will be monitored.
 
Given the increases in anti-KLH IgM and IgG responses observed in cynomolgus monkeys, there is a theoretical potential for an enhanced response to vaccination, which has not yet been evaluated in clinical studies. The implications of this are not known but are not considered high risk. Investigators will counsel participants regarding the possible impact on vaccination (both of potential reduced responsiveness and enhanced reaction).
 |

| Potential Risk of Clinical Significance | Summary of Data/Rationale for Risk Refer to GSK2831781 IB for details. | Mitigation Strategy |
|--|--|--|
| | 
Clinical: No autoimmune phenomena were observed in the FTIH study 200630. In patients who received GSK2831781, clinical activity scores for psoriasis (a T cell-mediated disease) tended to improve over the time course of exposure to GSK2831781.
 | |
| Reproductive Toxicity | 
Non-clinical: Whereas there are no data for the drug class or mode of action pointing to a known pregnancy hazard, no animal reproduction testing has been conducted. Therefore, there is the potential for unidentified risks to the embryo-foetus or pregnancy.
 
Doses up to 100 mg/kg/week for 26-weeks did not result in pathology in the reproductive organs of mature monkeys or effects on spermatogenesis staging.
 
Clinical: The IMP level of monoclonal antibody (mAb) in human semen is expected to be too low to be of concern.
 | 
The study will recruit only male participants.
 
There are no specific contraception requirements for males participating in this study.
 |

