8.2. Study Stopping Criteria

8.2.1. Serious Adverse Events

If one or more participants experience an SAE in either Part A or Part B of the study that can be reasonably attributed to GSK2831781, and which is not a subcutaneous injection site reaction, no further participants will be dosed until a full safety review has taken place and the study will be temporarily halted.

If one or more participants in Part B experience an SAE due to a SC injection site reaction, no further participants will be dosed in Part B until a full safety review has taken place, although dosing in Part A may continue.

Relevant reporting and discussion with the GSK2831781 Safety Review Team (SRT; see Section 8.3 for additional details), relevant GSK personnel, and with the Ethics Committee and Regulatory Agency will then take place. If, following the safety review, a decision is made to restart dosing (which may be at either the same dose or a lower dose), this will only occur after approval of a substantial amendment.

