8.2.2. AEs of Special Interest

The following events of note across both Part A and Part B will result in review by the SRT before further participants are dosed:

- A severe opportunistic or atypical infection.
- Cytokine release syndrome of Common Terminology Criteria for Adverse Events (CTCAE) (Version 5) Grade ≥ 2 .
- Serum sickness of CTCAE (Version 5) Grade ≥ 2 .
- A neutrophil count $< 0.5 \times 10^9/L$ on any occasion (confirmed on repeat testing within 3-5 days), an absolute neutrophil count $< 1.0 \times 10^9/L$ for 2 weeks, or CTCAE Grade 3 febrile neutropaenia (neutrophil count $< 1.0 \times 10^9/L$ and fever $\geq 38.5^\circ C$).

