8.2.3. Liver Chemistry Criteria

Liver chemistry study stopping criteria, and individual participant increased monitoring criteria, have been designed to assure participant safety and evaluate liver event aetiology.

- Liver events meeting SAE criteria will be managed as detailed in Section 11.5.

- Liver events characterized by an ALT ≥ 3 x ULN but not meeting SAE criteria, if reasonably attributable to GSK2831781, will result in review by the SRT before further participants are dosed and additional assessments as detailed in Section 11.5.

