8.2.4. QTc Criteria

QTc study stopping criteria, and individual participant increased monitoring criteria, have been designed to assure participant safety. The *same* QT correction formula *must* be used for *each individual participant* to determine eligibility for and discontinuation from the study. Use of Fridericia's formula (QTcF) is preferred in this study. The formula may not be changed or substituted once the participant has been enrolled; for example, if a participant is eligible for the protocol based on QTcF, then QTcF must be used for discontinuation of this individual participant as well. Safety ECGs and other non-protocol specified ECGs are an exception.

If a participant meets any of the criteria below, this will result in review by the SRT before further participants are dosed, as well as additional monitoring of the affected individual:

- QTc >500 msec.
- Uncorrected QT >600 msec.
- Change from baseline of QTc >60 msec.

With the exception of screening, the QTc should be based on single ECG reading. If an ECG demonstrates a prolonged QTc interval, then a further two ECG readings should be obtained over a brief recording period and the averaged QTc interval used to determine whether the participant meets the criteria to trigger SRT review and for individual further monitoring. Further monitoring will consist at minimum of triplicate ECGs one week later, and then follow-up until values are no longer clinically significant.

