| 
Other situations:
 
 ● Medical or scientific judgment should be exercised in deciding whether SAE reporting is appropriate in other situations such as important medical events that may not be immediately life-threatening or result in death or hospitalization but may jeopardize the participant or may require medical or surgical intervention to prevent one of the other outcomes listed in the above definition. These events should usually be considered serious. 
Examples of such events include invasive or malignant cancers, intensive treatment
 |

in an emergency room or at home for allergic bronchospasm, blood dyscrasias or convulsions that do not result in hospitalization, or development of drug dependency or drug abuse.

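### Section 3.3.1 relies on stopping criteria for hypersensitivity, but no rule in Section 8.2 holds dosing after a single attributable, non-serious acute reaction

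*Protocol*

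**What the plan says.** The protocol's risk table (Section 3.3.1) has eight rows, and two of them cite stopping criteria as a mitigation. The neutropaenia row cites "Haematological stopping criteria". The infusion reaction/hypersensitivity row cites "Exclusion criteria, stopping criteria and appropriate treatment for hypersensitivity reactions".

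The study-level rules are in Section 8.2:

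- **8.2.1** applies when one or more participants "experience an SAE in either Part A or Part B of the study that can be reasonably attributed to GSK2831781". Injection-site SAEs in Part B have their own rule.
- **8.2.2** begins "The following events of note across both Part A and Part B will result in review by the SRT before further participants are dosed". It lists severe opportunistic or atypical infection, CRS of Grade 2 or above, "Serum sickness of CTCAE (Version 5) Grade" 2 or above, and neutrophil thresholds.
- **8.2.3** provides that ALT of at least 3x ULN "but not meeting SAE criteria, if reasonably attributable to GSK2831781, will result in review by the SRT before further participants are dosed".
- **8.2.4** sets three QT/QTc limits and says "If a participant meets any of the criteria below, this will result in review by the SRT before further participants are dosed".

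Section 7.7, echoed in 8.3, adds SRT review in two further situations: moderate or severe AEs that recur across participants in a cohort or stratum, and attributable pharmacological effects judged unacceptable. Sections 9.1.5 and 9.1.6 describe clinical management of infusion and hypersensitivity reactions.

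**The concern.** The risk table counts stopping criteria among the protections against hypersensitivity, but Section 8.2 has no criterion for it. The rules for the first participants make this matter. In Part A (5.5.1) the remaining participants may be dosed if nothing has met the Section 8 criteria. In Part B (5.5.2) they are dosed after a 46-hour review of sentinel data unless those criteria have been met. An event outside Section 8.2 therefore does not, by rule, close either gate.

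At stake is whether an early isolated reaction in a healthy volunteer must be looked at before the next person is dosed. Section 5.5 describes this as the first use of 450 mg in healthy participants and the first subcutaneous use in humans.

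**Working it through.** No figure stated in the plan is in dispute. The check is a reading of every rule that could hold dosing, followed by two counts and an illustration.

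**1. Does any rule reach one attributable, non-serious, moderate acute allergic reaction?**

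| Rule | Reaches it? | Why |
|---|---|---|
| 8.2.1 | No | Requires an SAE |
| 8.2.2 | No | Only if diagnosed as CRS or serum sickness |
| 8.2.3, 8.2.4 | No | ALT and QT/QTc only |
| 7.7, recurrence limb | No | One case is not recurrence across participants |
| 7.7, pharmacological limb | Not clearly | Term undefined; an allergic reaction is not plainly a pharmacological effect |
| 8.3 | At discretion | Repeats the triggers above; otherwise review as needed |
| 9.1.5, 9.1.6 | No | Care of the affected participant only |

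Section 9.1.6 lets a dose be restarted after a mild reaction and stops it for a severe one. It gives no rule for a moderate reaction, and Section 8.1 adds none.

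**2. How much is already covered?** Section 11.3.2 usually treats as serious "important medical events that may not be immediately life-threatening or result in death or hospitalization but may jeopardize the participant", and names intensively treated allergic bronchospasm as an example. Most severe reactions therefore fall under 8.2.1. The CRS symptoms in 3.3.1 include rash, tongue and throat swelling and dyspnoea, so some allergic reactions may be caught as suspected CRS. The remainder is mostly moderate. A severe but non-serious case is possible, since 11.3.3 separates intensity from seriousness, but it would be unusual.

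**3. Trigger count.** Hold triggers that need no SAE, by bullet: 4 (8.2.2) + 1 (8.2.3) + 3 (8.2.4) = 8. The neutrophil bullet contains three alternatives, so counting those separately gives 8 − 1 + 3 = 10. On either count, none names acute hypersensitivity. Of the two risk rows that cite stopping criteria, neutropaenia has explicit thresholds in 8.2.2 and hypersensitivity has none.

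**4. Active participants dosed after the gates.** Inputs are the 6:2 allocation per stratum in Part A, 8:8:4 in Part B, and the sentinel rules.

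- Part A: when one stratum reaches 3 dosed, the other has 0 to 2, so 3 to 5 have been dosed. Each stratum has only 2 placebo, so 1 to 5 of these are active. Active remaining: 12 − (1 to 5) = 7 to 11.
- Part B: the sentinels are one active (150 mg) and one placebo. Active remaining: (8 − 1) + 8 = 15.
- Total: 15 + (7 to 11) = 22 to 26 of 12 + 16 = 28.

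**5. Illustration.** The documents give no reaction rate, so p below is assumed. The chance of exactly one case among n active participants is n·p·(1 − p)^(n−1). For n = 12 and p = 0.05 this is 12 × 0.05 × 0.95^11 = 0.341.

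| n active | p = 0.02 | p = 0.05 | p = 0.10 | p = 0.20 |
|---|---|---|---|---|
| 6 (one Part A stratum) | 0.108 | 0.232 | 0.354 | 0.393 |
| 12 (Part A) | 0.192 | 0.341 | 0.377 | 0.206 |
| 28 (all) | 0.325 | 0.350 | 0.163 | 0.014 |

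If such reactions occur at all, a single isolated case, which the recurrence limb of 7.7 does not reach, is a plausible outcome over much of this range.

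**The case against.** The strongest reply is that nothing is contradicted. Section 3.3.1 does not promise a dedicated trigger or a non-serious threshold. One attributable SAE already halts dosing, and the phrase may simply mean stopping that participant's dose. On this view the sponsor chose a graded scheme, with seriousness for a single case and recurrence for moderate or severe events. ALT, QTc and neutrophil limits are weak precedents because those abnormalities can be silent, whereas an acute reaction is visible in a participant resident for 24 hours. Early Part A doses are at least 22 hours apart, the Part B sentinel data must be reviewed, and the SRT can meet when needed.

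Part of this stands. Serious reactions are covered, recurrent ones are covered, and an acute event would probably be noticed. The count of 22 to 26 describes the design and does not estimate harm.

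The rest does not remove the gap. The parallel neutropaenia entry corresponds to a study-level rule in 8.2.2, so a study-level reading is the natural one here too. Even on the individual reading, no rule covers a moderate reaction. CRS and serum sickness are clinical diagnoses, not silent laboratory findings, and they hold dosing at Grade 2. Being noticed is not the same as requiring SRT review: Section 5.5.2 does not say who reviews the Part B sentinel data, and its default is to proceed unless the stopping criteria are met.

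**Conclusion.** The concern holds. Section 3.3.1 cites a safeguard that Section 8.2 supplies only for serious reactions or those diagnosed as CRS or serum sickness. One attributable, non-serious acute hypersensitivity reaction does not require SRT review before further dosing, whereas eight other bulleted non-SAE triggers do so on a single participant.

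The gap is narrow and would rarely matter. The first-in-human study reported no infusion or hypersensitivity reactions. The Part B sentinel is also not the only systemic check: all Part A Caucasian participants, up to 6 of them on active 450 mg IV, are recruited before Part B recruitment may start. No endpoint or analysis is affected. The change is recommended because the participants are healthy and the correction is small.

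The conclusion rests on two assumptions: that the pharmacological-effects limb of 7.7 is not meant to include allergy, and that the SRT charter, which is not among these documents, has no such trigger.

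**What to change.** Add one item to the Section 8.2.2 list, at the grade already used there for CRS and serum sickness:

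> Acute systemic hypersensitivity reaction (see Section 9.1.6), during infusion or after SC injection, of CTCAE (Version 5) Grade 2 or above and reasonably attributable to GSK2831781. Local infusion-site reactions (Section 9.1.5) and injection-site reactions are excluded.

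The symptom list in 9.1.6 includes non-specific items such as flushing and vomiting, so the sponsor should also state which CTCAE terms count. Both gates pick up the new item through Section 8 without further edits. If the sponsor prefers not to add it, Section 3.3.1 should say that the stopping criteria cover only serious reactions and those diagnosed as CRS or serum sickness.

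The cost is a protocol amendment with ethics committee approval (11.1.1), then an occasional SRT review and a short pause in dosing. Because attribution is made blinded, some reviews will concern placebo participants. A review alone does not bring in the substantial amendment required by 8.3; that follows only if the study is actually halted for safety.
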